6 AIMS AND OBJECTIVE

The overarching research question is whether in addition to the usual standard support, a client-centred intervention with behavioural support to reduce smoking and promote physical activity, for smokers wishing to reduce smoking with no immediate plans to quit (but who may be open to the notion of quitting), can increase CO-confirmed prolonged abstinence at 9 months post baseline (i.e. 6 months post intervention) compared to standard support alone, and whether such an intervention is cost-effective.

The aims of the trial are as follows:

[figure not shown]
- To determine whether the additional behavioural support for an intervention promoting smoking reduction and increasing physical activity, compared to support as usual (SAU), significantly increases the proportion of participants who achieve prolonged abstinence at 9 months post baseline as confirmed by the concentrations of their expired CO.
- To determine whether the intervention, compared to SAU, increases the proportion of participants who reduce self-reported cigarette smoking by at least 50% at 3 and 9 months post baseline compared to baseline smoking levels, while quantifying the use of licenced nicotine containing products (LNCPs) and e-cigarettes.
- To determine whether the intervention, compared to SAU, increases the proportion of participants who achieve CO-confirmed prolonged abstinence at 15 months post baseline (i.e., 12 months post intervention).
- To determine whether the intervention, compared to SAU, increases self-reported physical activity at 3 and 9 months post baseline, and accelerometer assessed physical activity at 3 months post baseline.
- To determine whether the intervention, compared to SAU, improves quality of life (SF 12, EQ-5D-5L), weight and cigarette cravings at 3 and 9 months post baseline.
- To estimate the additional resource use and costs of delivering the intervention and to estimate
 the differences in health and social care service utilisation and the related costs between
 intervention and SAU at 9 months post baseline.

- To estimate the cost-effectiveness of the intervention compared with SAU at (i) 9 months (incremental cost per unit change in abstinence rate, and cost per quality adjusted life year [QALY] gained) and (ii) over a longer term / lifetime horizon (incremental cost per life year saved, per QALY gained) extrapolating beyond the trial using a previously developed decision-analytic model to estimate future costs and benefits.

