7.5 Secondary outcomes

Point prevalence CO verified abstinence at 3, 9 and 15 months post baseline

Only those reporting abstinence by mailed survey at 3 and 9 months will be contacted for CO verification. Only those abstinent at 9 months will be followed up at 15 months by mailed questionnaires and if abstinent by face-to-face assessment of expired CO.

Self-reported smoking and use of aids to reduce/quit smoking

Study participants will be asked to self-report the number of cigarettes smoked and type of nicotine product, i.e. pipes, cigars and roll your own. The same formula used in the EARS pilot study will be used to convert amount of loose tobacco into number of cigarettes [1].

Questions to capture use of e-cigarettes and NRT (nicotine replacement therapy) products

Physical activity

Questions at baseline, 3 and 9 months will assess self-reported 7-day physical activity recall. A sub set of all participants in the TARS study will be invited to wear an accelerometer for a 7 day period during the study. The accelerometer, and instructions for use will be mailed to selected participants at the 3 month time point from CTU, along with the 3 month questionnaire booklet. The accelerometer is waterproof, and is worn continuously for 7 days. At the end of the 7 days the participant should return the accelerometer to the CTU in the freepost envelope provided.

Self-reported height and weight - Body Mass Index (BMI)

At baseline, 3 and 9 months participants will be asked to self-report their height and weight. The questions will be part of the questionnaire booklet mailed to participants from CTU at baseline, 3 and 9 months. Based on the weight and height reported we will derive a measure of BMI.

Health related quality of life (EQ-5D-5L & SF-12)

EQ-5D-5L

This is described in section 19.1.

SF-12

The SF-12 is a 12-item, patient-reported survey of patient health, consisting of twelve questions [70]. In this study participants will be asked to complete the SF12 as part of the questionnaire booklet mailed to them from CTU at baseline, and then at 3 months follow-up and 9 months follow-up.

Health economic outcomes

Health service utilisation and costs, including smoking related costs

Process measures

The following process measures will also be assessed as part of the self-report questionnaire booklets issued to all participants by CTU at the baseline and 3 months:

- Importance and confidence in smoking reduction and cessation

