17 STATISTICAL CONSIDERATIONS

17.1 Sample Size

Since the primary analysis is a comparison in each allocated group of the proportions of the primary binary outcome, the sample size is calculated for a two-sided Fisher exact test. An abstinence rate of 5% for the control group, and detectable effect of 6% (i.e.: an increase from 5% to 11% due to the intervention) are conservative estimates consistent with those from the EARS pilot study and those reported from a systematic review of pharmacological interventions. The corresponding odds ratio for this effect is 2.35. Participants with missing outcome data will be assumed to be still smoking, and the number of participants in each allocated group are assumed to be in the ratio of 1:1. Under these conditions, according to Stata v14.2, the minimum number of participants required to detect an abstinence rate of 11% compared to that of 5% in the control group with a significance level of no more than 5% and power of at least 90% is exactly 900, above which a power in excess of 90% is maintained (Figure 1). The Stata code and the R code used to verify this calculation is found in Appendix 2.

TARS Protocol Version 2 26OCT2017

[figure not shown]

Figure 1: Plot of power of test afforded by each sample size ranging from 884 to 916, for equal group sizes and 5% significance level, where the proportion of CO-confirmed abstinence rates at 9 months is 0.05 and 0.11 in the control and intervention group, respectively.

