17.2.4 Analysis of secondary outcomes

Between-group comparisons will be undertaken at 3 and 9 months post baseline for all available outcome measures, and only prolonged abstinence rates at 15 months. Analysis will use multivariable logistic regression to compare these secondary outcomes between allocated groups, with adjustment for the stratification factors [site, HSI], as well as important baseline covariates (i.e. age, gender, socio-economic status, level of smoking, recent quit attempts).

The between-group comparisons of continuous outcomes (e.g. daily cigarettes smoked, minutes of MVPA) will be reported as mean differences together with 95% confidence intervals, unless the outcomes are substantially skewed. Multi-variable linear regression will be used to compare continuous variables between allocated groups, with adjustment for the stratification factors, important baseline covariates, and baseline outcome values, where relevant.

Sensitivity analysis will examine the potential influence of participants lost to follow-up under varying assumptions. Further sensitivity analysis may be undertaken if any marked imbalance between allocated groups is seen in important baseline characteristics, by further adjustment for such baseline characteristics in the multi-variable models detailed above.

Finally, we will conduct exploratory mediational analysis to determine if any effect of trial arm on the primary outcome was mediated by changes in smoking, physical activity, from baseline to 3 months. We will also examine if changes in smoking and physical activity are mediated by changes in various secondary outcomes (eg, importance and confidence to reduce smoking/increase physical activity; self-monitoring and goal setting; cravings)

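### As written, the 3-month accelerometer comparison carries no prior-activity covariate, although 7-day activity recall is collected before randomisation

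*Protocol*

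**What the plan says.** - **Aim.** Protocol section 6 makes "accelerometer assessed physical activity at 3 months post baseline" part of a trial aim, alongside self-reported activity at 3 and 9 months.
- **Who wears the device, and when.** Section 7.5 states: "A sub set of all participants in the TARS study will be invited to wear an accelerometer". The device is posted with the 3-month booklet, and the schedule in section 10.6 marks it at month 3 only. The size of the subset is not given.
- **What is known before randomisation.** Section 8.7 lists the 7-day activity recall in the baseline booklet and makes randomisation conditional on the CTU receiving that booklet completed.
- **Adjustment.** For continuous outcomes, section 17.2.4 adjusts for the stratification factors, "important baseline covariates, and baseline outcome values, where relevant". Earlier in the same section the important covariates are given as a closed list: age, gender, socio-economic status, level of smoking and recent quit attempts. None measures activity.
- **Other uses of baseline activity.** Section 17.2.3 names MVPA level as a possible effect modifier. Sections 17.2.4 and 18.3 use change in activity from baseline to 3 months in mediation analyses. Baseline recall is also the natural baseline value for the self-reported activity outcome.

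**The concern.** The rule in 17.2.4 works for outcomes measured at baseline and at follow-up. For the accelerometer outcome the baseline term has nothing to supply, and no listed covariate stands in for it. Self-reported activity would therefore be adjusted for prior activity, while device-measured activity would not.

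The accelerometer is the trial's only device-based evidence on whether the activity part of the intervention changed behaviour; the other measure is self-report by participants who know their allocation (section 8.8). Its precision is already limited. Only a subset is invited, section 10.1 offers no extra incentive for returning the device, and section 10.4 expects 60-65% to complete follow-up at 3 months. A covariate likely to predict the outcome, and already collected, is worth using here.

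**Working it through.** **1. The plan's own figure.** The protocol gives no sample size, standard deviation or power for the accelerometer outcome. Its only sample-size figure is for the primary outcome. In section 17.1 "the sample size is calculated for a two-sided Fisher exact test", for 5% versus 11% with 1:1 allocation, and the total "with a significance level of no more than 5% and power of at least 90% is exactly 900". Enumerating the exact power over both binomial distributions gives 0.8996 at N = 898 and 0.9003 at N = 900, and power stays above 0.90 up to N = 916. The odds ratio is (0.11/0.89)/(0.05/0.95) = 2.348, which matches the stated 2.35. Both figures reproduce, and the present point does not touch them.

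**2. Covariates available to the accelerometer model as written.**

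| Term in 17.2.4 | Available for this outcome? | Measures activity? |
|---|---|---|
| Site, HSI | yes | no |
| Age, gender, socio-economic status, level of smoking, recent quit attempts | yes | no |
| Baseline value of the outcome | no, no baseline wear | not applicable |
| Baseline 7-day recall | collected, but not named for this outcome | yes |

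**3. What adding recall would gain.** Let r be the partial correlation between baseline recall and 3-month accelerometer activity, given the covariates already in the model. The protocol gives no r, so 0.2 to 0.5 is an assumption.

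- Residual variance is multiplied by 1 − r².
- Confidence interval width is multiplied by √(1 − r²).
- The gain in effective sample size is 1/(1 − r²) − 1.
- Power, for a comparison that has 80% without recall, is Φ[(1.960 + 0.842)/√(1 − r²) − 1.960].

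| Assumed partial r | 1 − r² | CI width × | Effective N | Power, from 80% |
|---|---|---|---|---|
| 0.2 | 0.96 | 0.980 | +4.2% | 81.6% |
| 0.3 | 0.91 | 0.954 | +9.9% | 83.6% |
| 0.4 | 0.84 | 0.917 | +19.0% | 86.4% |
| 0.5 | 0.75 | 0.866 | +33.3% | 89.9% |

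**4. Illustration in outcome units.** Assume 200 wearers in total, 100 per arm (the protocol does not give this number). The difference detectable with 80% power is (1.960 + 0.842) × √(2/100) × √(1 − r²) standard deviations. This is 0.396 with no activity covariate, and 0.388, 0.378, 0.363 and 0.343 at r = 0.2, 0.3, 0.4 and 0.5.

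**5. Missing recall.** Section 16.6 says questionnaire data will not be queried with participants, so a booklet may arrive with recall items blank. If a fraction m of wearers lacks recall and is dropped, effective sample size is multiplied by (1 − m)/(1 − r²). This falls below 1 once m exceeds r²: 4% missing at r = 0.2, 9% at r = 0.3. The covariate therefore helps reliably only with a rule that keeps those wearers in the model.

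**The case against.** The strongest reply has four parts.

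- **This belongs in the statistical analysis plan.** Section 20.5 confirms that one is to be agreed with the DMC, and it may name recall. That plan was not available here. However, the protocol does not leave the adjustment set open: it closes the covariate list and adds a baseline rule that supplies nothing for this outcome. The point is about a stated set that could be better, not about missing detail.
- **The wording allows recall as a proxy.** Section 17.2.4 speaks of baseline outcome values where relevant and gives minutes of MVPA as an example without separating device from recall. That reading is possible, but the text does not say it. A clarifying sentence settles it.
- **Imbalance is already covered.** Section 17.2.4 allows further adjustment if marked baseline imbalance is seen. That step is optional, depends on the data and is only a sensitivity analysis, so it does not replace a covariate fixed in advance.
- **The gain may be small.** This stands. At r = 0.2 the interval narrows by 2%.

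Three stronger readings are tempting, and the protocol does not support them. A reader might infer that the plan adjusts only for baseline values of the same outcome; in fact site, HSI and five other covariates are in the model. A reader might infer that baseline recall goes unused; it is merely unnamed for this comparison. A reader might infer that the accelerometer result would be biased. Under randomisation, omitting a prognostic covariate from a linear model costs precision only. Bias would need device return to depend on prior activity differently by arm. Nothing in the protocol shows that, and section 13 plans two reminder letters and a telephone call for unreturned devices.

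**Conclusion.** The point holds as a low-severity improvement to one secondary outcome. As written, the 3-month accelerometer comparison has no prior-activity covariate, while a suitable one is collected before allocation.

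The size rests entirely on an assumed partial correlation. For 0.2 to 0.5, effective sample size rises by about 4% to 33% and the confidence interval narrows by about 2% to 13%. The calculation also assumes a linear model with a roughly linear relation after any transformation, and no loss of wearers through missing recall. The protocol gives no correlation, standard deviation or subset size from which to narrow the range. The validity of the comparison, the primary analysis and the total of 900 are not in question.

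**What to change.** Add to section 17.2.4 that the 3-month accelerometer outcomes are adjusted for baseline self-reported 7-day recall activity, in addition to site, HSI and the listed covariates. State in the same place:

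- the form in which recall enters the model, for example log-transformed if skew is expected, fixed before the data are seen;
- that missing baseline recall is filled by a simple imputation that ignores trial arm and outcome, such as the overall baseline mean, so that no wearer is dropped.

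If the statistical analysis plan already names this covariate, a cross-reference is enough. The change needs no new data collection and no change to the sample size. Its cost is one or two sentences, one degree of freedom in the model and the imputation rule.

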7.4 Primary outcome

Carbon monoxide (CO) verified prolonged abstinence over 6 months

We will use guidance provided by Aveyard *et al* (2009) [75] on floating prolonged abstinence. Study participants who report abstinence on the 3 month mailed survey (which is confirmed by face to face CO expired air assessment) and then again self-report abstinence (and not having smoked even a puff since the 3 month assessment) on the 9 month mailed survey (which is again confirmed by CO expired air assessment), will be identified as having prolonged abstinence over at least 6 months.

The CO monitor used in this study is a Bedfont Micro CO monitor. The CO measurement involves the participant holding their breath for 10-15 seconds, and then blowing into the monitor. The carbon monoxide value in parts per million (ppm) is shown with values below 10 ppm indicating abstinence. The reading at each recruitment site will be reported remotely into the on-line PenCTU data management system. The CO monitor will be regularly calibrated to ensure accurate measures.

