9 INTERVENTION

9.1 TARS Intervention

Participants in the intervention arm will be offered open-ended support from a Health Trainer (HT) which will broadly include the content described in Table 1 below. In the interests of ensuring it meets the participants needs the HT will suggest options for the support provided but empower the participant to decide what support is offered, where and when. In the pilot EARS trial participants had an average 4.2 sessions by phone or face to face with the HT with a range of 0-8 [1]. If a smoker wishes to quit at any time during the 8 week intervention period, they will be offered 6 weeks of additional behavioural and motivational support from the HT, as well as support to access services as part of usual care to stop smoking (as available at each location) if desired. If a smoker wishes to reduce smoking using e-cigarettes or licenced nicotine containing products (LNCP) they will also be offered any local available support for this. Typically, there are no formal programmes for use of medication during reduction and people usually buy their own NRT or, more often, e-cigarette or vaper product. We will also monitor any national guidelines (eg, NICE PH45 guidelines for smoking harm reduction) for any changes and adopt our actions and guidance accordingly throughout the trial.

The goal of the intervention is to promote motivation to make a quit attempt. If a smoker wishes to quit at any time during the 8 week intervention period, they will be recommended to attend a stop

smoking service, where they will be offered and pharmacological and behavioural support that comprises usual smoking cessation practice. If the participant prefers, the health trainer could continue to provide cessation support and recommend options for use of pharmacotherapy.

Intervention components	Aim	Content	Process and outcome evaluation
Active participant involvement (1)	Develop rapport, build trust, and shared respect.	Effective communication skills. Build autonomous support.	Participant feedback on HT-led support.

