9.2 Support as usual

Participants allocated to both arms of the trial will receive guidance for smoking reduction and cessation, including web links to what is offered at local level, or paper versions of this information. In the current financial climate and without clear evidence of benefit and a clear pathway of care, it

is unlikely that there will be much support for smoking reduction as described as usual care. Given the rapidly changing public health environment we do not propose to request approval for this guidance or amendments from the REC if and when changes occur to what is offered locally to prevent unnecessary delays to the trial but will be happy to forward versions as appropriate.

10 Follow-up Assessments – all participants

10.1 3 month follow-up assessments

The 3 month assessments will be mailed to participants in the form of a questionnaire booklet, with a cover letter, and freepost return envelope. An opportunity will be given for participants to complete the questionnaire booklet over the telephone with a member of the local research team if they would prefer. A subset of study participants will also receive an accelerometer by post, and instruction sheet at the 3 month time point.

The 3 month questionnaire booklet contains questions relating to the following:

- Smoking behaviour
- Importance and confidence in smoking reduction and cessation
- Importance and confidence in being physically active
- Availability of support to reduce smoking and increase physical activity
- Use of physical activity for smoking regulation
- Self-reported physical activity (7-day physical activity recall)
- Planning to change smoking
- · Planning to change physical activity
- Self-monitoring of smoking
- · Self-monitoring of physical activity
- Urge & strength of urge to smoke
- Use of e-cigarettes and NRT (nicotine replacement therapy) products
- Health related quality of life (EQ-5D-5L & SF12)
- Physical activity (accelerometer) (7 days)
- Self-reported height and weight (BMI)
- Health service utilisation and costs, including smoking related costs
- Serious adverse event reporting

Participants who self-report that they have quit will be invited to attend a face-to-face assessment, which will include the following additional assessments:

- Self-reported prolonged abstinence (since last quit attempt, with date, if relevant)
- Expired carbon monoxide (CO) measurement

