17.2.2 Primary analysis of primary outcome

The primary analysis will be a logistic comparison of the primary outcome of CO-confirmed abstinence at 3 and 9 months post-baseline, using a mixed-effects model to account for clustering by site, with the adjustment for the HSI stratification factor, as well as important baseline covariates (i.e. age, gender, socio-economic status, level of smoking, recent quit attempts. Interpretation of the

TARS Protocol Version 2 26OCT2017

primary effectiveness will be based on the adjusted odds ratio from this model, and the point estimates reported with 95% confidence intervals. Those participants with missing outcome data will be assumed to be still smoking [6].

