17.2.3 Secondary analysis of primary outcome

Although the trial is not powered to detect the influence of moderating factors on the primary or secondary outcomes, secondary analyses will be undertaken to explore whether the intervention effect is modified by sociodemographic and/or behavioural factors (e.g. age, gender, socio-economic status, baseline HSI, MVPA level, and confidence to quit). These analyses will be undertaken for the primary outcome and for the reduction in smoking (both the actual reduction and the proportion of participants reporting \geq 50% reduction in smoking level). The multi-variable models outlined above will be extended to include the interaction term of allocated group and the potential modifying variable, tested at the 1% significance level. However, such analyses will have low statistical power and likely to yield false positive findings, so the results will need to be conservatively interpreted. We will also conduct a sensitivity analysis to determine if the intervention dose actually received influenced differences in outcomes.

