18.3 Analysis

Qualitative data will be subject to thematic analysis using constant comparison techniques to extract concepts and themes [76] (and using NVivo to manage the data). The transcripts relating to smoker experiences of the intervention will also be analysed to produce a sample of individual narratives, allowing an increased insight into the processes of intervention engagement and the processes of supporting behaviour change [77]. Second coding of a sample of the transcripts and discussion of the emerging coding framework, as well as techniques such as negative case-finding and hypothesis testing will be used to increase the depth of analysis and enhance the likely objectivity of interpretation [79].

As reported in the section above on secondary outcomes, we will examine changes in smoking and physical activity and related beliefs, as well as information about intervention engagement. We will conduct exploratory mediation analysis to determine if changes between baseline and 3 months in items to assess behaviour change constructs (ie, perceived importance and confidence to change smoking and physical activity, availability of support, use of physical activity to aid changes in smoking, urges and strength of urges to smoke, and self-monitoring and engagement in planning to change smoking and physical activity) mediate changes in smoking and physical activity.

19 ECONOMIC EVALUATION (Cost-Effectiveness Analyses)

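### The 3-month smoking mediator in section 17.2.4 contains a component of the primary outcome it is meant to explain

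*Protocol*

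**What the plan says.** Section 7.4 of the protocol defines success in two steps. "Study participants who report abstinence on the 3 month mailed survey (which is confirmed by face to face CO expired air assessment"), and who then report at 9 months not having smoked since, with a second CO confirmation, are the successes. Section 17.2.2 analyses the same quantity, the "primary outcome of CO-confirmed abstinence at 3 and 9 months post-baseline", and counts missing outcomes as smoking.

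Section 17.2.4 adds an exploratory mediation analysis to determine whether "any effect of trial arm on the primary outcome was mediated by changes in smoking, physical activity, from baseline to 3 months".

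The mediators come from the 3-month booklet. Section 10.1 introduces its list of contents with "The 3 month questionnaire booklet contains questions relating to the following"; the list includes smoking behaviour and the 7-day physical activity recall. A participant who reports having quit at this assessment is invited to the 3-month CO check.

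CO-verified point-prevalence abstinence at 9 months is a separate secondary outcome (section 7.5). Under section 10.2 anyone who reports having quit at 9 months is invited for CO measurement, whatever their status at 3 months. Nothing in the protocol text separates the smoking mediator from the 3-month part of the primary outcome.

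**The concern.** A mediator has to be distinct from the outcome and come before it. Here the smoking mediator at its maximum, complete reduction at 3 months, is also the first condition for success. An association between mediator and outcome then says little about mechanism, because the endpoint definition produces it.

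This touches a question the trial sets out to inform. Section 5.1.7 says there is little or no evidence that reduction helps cessation, section 14.4 says little is known about whether cutting down leads to quitting, and section 6 lists the exploration of mechanisms as an aim. A smoker who cuts down by month 3 and stops between months 3 and 9 follows exactly that route, yet scores as a failure on the primary outcome. The planned analysis cannot credit that route, and it can still report that reduction carried the effect.

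**Working it through.** **Inputs from the protocol.** Section 17.1: 5% against 11%, 1:1 allocation, 900 in total, two-sided Fisher exact test, odds ratio 2.35. These reproduce: exact power at 900 is 0.9003 (0.8996 at 898), and (0.11/0.89)/(0.05/0.95) = 2.348. Expected successes are 450 × 0.05 = 22.5 and 450 × 0.11 = 49.5.

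**Step 1: what the definition fixes.** Let A3 be CO-confirmed abstinence at 3 months and A9 be abstinence maintained from then and CO-confirmed at 9 months. Success is Y = A3 × A9, so P(Y = 1 | smoking at 3 months) = 0. All of the expected 22.5 + 49.5 = 72 successes have 100% reduction.

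In a logistic model with proportional reduction M, write the linear predictor as α + c(M − 1), with any arm term added. Raising c leaves everyone at M = 1 unchanged and improves the fit for everyone below 1, all of whom have Y = 0. The slope c therefore has no finite maximum-likelihood estimate. The same holds for absolute change in cigarettes if baseline consumption is in the model, since baseline minus change is 3-month consumption.

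**Step 2: what the definition does not fix.** P(Y | arm) = P(A3 | arm) × P(A9 | A3, arm). The indirect effect through A3 is the arm difference in P(A3) times the retention rate, in the control or the intervention arm. The 3-month and retention rates below are assumptions, chosen to return 5% and 11%; the total effect is 0.060 in each row.

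| Assumed source of the effect | A3, control / intervention | Retention, control / intervention | Indirect effect | Share |
|---|---|---|---|---|
| Quitting by 3 months only | 7.1% / 15.7% | 70% / 70% | 0.060 | 100% |
| Maintenance only | 15% / 15% | 33.3% / 73.3% | 0 | 0% |
| Mixed | 10% / 15% | 50% / 73.3% | 0.05 × 0.50 = 0.025, or 0.05 × 0.733 = 0.037 | 42% or 61% |
| Fewer early quits, better maintenance | 20% / 15% | 25% / 73.3% | −0.05 × 0.25 = −0.013, or −0.05 × 0.733 = −0.037 | −21% or −61% |

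**Step 3: what a product-of-coefficients analysis would report.** Simulation of 1,000 trials per scenario, 450 per arm. The mediator is the fractional reduction at 3 months: 1 if abstinent, otherwise mean 0.25 and SD 0.25, cut off at −0.3 and 0.95. The outcome path used a linear probability model with arm. The joint test requires both the arm-mediator and the mediator-outcome path to be significant at 5%. All mediator values are taken as observed, although section 10.4 expects 60-65% completion at 3 months. Extra reduction means 0.10 more among non-quitters in the intervention arm, with no bearing on Y. The scenarios with no effect on outcome use 8% abstinent at 3 months and 70% retention in both arms.

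| Scenario | True share | Mediator-outcome path significant | Joint test significant | Median estimated share |
|---|---|---|---|---|
| Quitting by 3 months only | 100% | 100% | 81.9% | 50% |
| Maintenance only | 0% | 100% | 5.3% | 0% |
| Maintenance only, plus extra reduction | 0% | 100% | 96.7% | 55% |
| No effect on outcome, plus extra reduction | none | 100% | 99.3% | not meaningful |
| No effect at all | none | 100% | 5.8% | not meaningful |

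The mediator-outcome path was significant in every run, including runs with no arm effect on the outcome. The estimated share was about the same (50% and 55%) when the true share was 100% and when it was 0%.

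**Step 4: is an arm difference in partial reduction plausible?** Section 5.1.6 reports that 39% against 20% in the pilot cut down by at least half, and 10% against 4% were abstinent at 16 weeks. If all abstainers are among the reducers, 39 − 10 = 29% against 20 − 4 = 16% reduced without quitting. The time point of the reduction figures is not given there, so this is only indicative.

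**The case against.** The strongest objection is that only one of the two paths is fixed. A reader might infer that mediation is guaranteed, or near-complete whatever the mechanism. The definition does not support that: if the arms differ only in maintenance after month 3, the indirect effect is zero and the joint test rejects at about its nominal rate. This objection stands and limits the point. It does not remove the overlap, nor the false indirect effect once the arms also differ in partial reduction.

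The analysis is also labelled exploratory, and the mechanism aim draws on interviews and fidelity data as well. That bears on severity. Leaving detail to an analysis plan does not answer the point, because the protocol itself pairs this mediator with this outcome.

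Three further readings are tempting but not supported:

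- **Physical activity.** Activity change is not part of the outcome. Its weakness is that it is measured at the time of the first abstinence check, so it may follow quitting rather than precede it.
- **The second set of mediation analyses.** Section 17.2.4 says "We will also examine if changes in smoking and physical activity are mediated by changes in various secondary outcomes", and section 18.3 asks whether 3-month changes in process items "mediate changes in smoking and physical activity". The primary outcome is not involved. Section 18.3 sets no time point for the smoking and activity changes being explained, and both are also collected at 9 months.
- **The dose analysis.** Section 17.2.3 plans "to determine if the intervention dose actually received influenced differences in outcomes", and section 9.1 says of those who wish to quit that "they will be offered 6 weeks of additional behavioural and motivational support from the HT". Dose does not enter the outcome definition, so there is no circularity. The offer follows a wish to quit, including attempts that fail, and time on offer is not dose received. Reverse causation is possible, but no method is stated that could be called wrong.

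**Conclusion.** The point holds for one sentence of section 17.2.4. Change in smoking to 3 months contains a component of the primary outcome, so the mediator-outcome path is partly definitional, a logistic outcome model is near-separated, and the reduce-then-quit-later route is coded as failure. A result of mediation by smoking change could not be read as evidence that reduction led to cessation.

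The zero probability of success for 3-month smokers follows from the definition alone. The sizes do not: the 3-month and retention rates, the distribution of reduction and the 10-point difference are assumptions, and the simulation used a linear model with complete mediator data. They show what can happen, not what will.

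Severity is low to moderate. The analysis is exploratory, and the primary test, sample size and error rate are untouched.

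**What to change.** In section 17.2.4, change the outcome of the first mediation analysis to CO-verified point-prevalence abstinence at 9 months, for both the smoking and the physical activity mediators measured at 3 months. A 3-month smoker can then become a success, and the mediators precede the outcome by six months.

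If the primary outcome is kept, report the smoking result only as a split: the arm difference in CO-confirmed quitting by 3 months, and the arm difference in maintenance from 3 to 9 months among those who had quit. The second part compares subgroups formed after randomisation and should be described as such.

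The cost is a change of wording before outcome data are seen; sections 7.5 and 10.2 already provide the data. The mediation outcome becomes less strict than the primary outcome, so its result explains a related effect and not the primary one. The change also does not settle whether activity change came before or after quitting in those who had already stopped by 3 months.
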